# Purpose and Rationale

The purpose of this study is to examine the impact of applying a menthol-based gel to the skin on human thermoregulation and thermal perception during exercise in the heat.

Transient receptor potential (TRP) channels are a family of membrane proteins evolved to interpret environmental stimuli through ion channels. One of these channels, the TRP melastatin 8 (TRPM8), is responsible for the sensation of innocuous cool temperatures and it might be responsible for noxious cold temperatures [1,2]. When applied topically, menthol acts upon a cold transduction enzyme to decrease the thermal sensitivity of TRPM8. This decreased thermal sensitivity allows activation of TRPM8 at warmer temperatures, mimicking a cool sensation in warm environments. This cool menthol feeling is used widely in everyday commercial products, but most popular when used as an analgesic in medicated pain-relieving gels/creams.

Current recommendations suggest menthol can be used as an ergogenic aid resulting in an improved performance within heated environments [1]. By decreasing thermal sensitivity of TRPM8 receptors, menthol exerts a physiological response that is perceived as external cooling. The most salient response is an increase in heat conservation, resulting in a reduced exercise capacity due to fatigue associated with a rise in core body temperature [3]. It seems

the application and concentration strength of menthol application to the skin may be the most obvious influential factors. As such, researchers have used proprietary menthol solutions with varying intensities (0.05- 10%) [1], yet, to our knowledge, no one has investigated widely available, over-the- counter products. Indeed, the translation from proprietary formula to over-the-counter application is unknown. Furthermore, it is unclear if currently available menthol products may also aid in performance. This incongruence requires further investigation into the effect of menthol on exercise performance.

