Following instrumentation, subjects will sit for 5 minutes as a baseline in a temperate environment. Immediately after, a researcher with gloved hands will topically apply BioFreeze or the control hypoallergenic cream from the shoulder to wrist and mid-thigh to ankle. Subjects will then enter the heat chamber (38°C, 60% relative humidity) and immediately begin a 30-minute walk on a treadmill (3.5 mph, 5% grade). Subjects will be intermittently asked to hold their arm steady for laser doppler flow collection (10, 20, 30 minutes). Subjects will also briefly pause at minute 10 in order to adhere an absorbent patch to their forehead for sweat collection over the following 10-20 minutes. Thermal perception using the ASHRAE scale (cold to hot) will be assessed pre and during exercise. After 30 minutes of walking, subjects will exit the chamber for removal of all skin and finger sensors. Subjects will then reenter the private room, remove their own rectal thermistor with gloved hands, and then a final nude body weight will be recorded after toweling off.

The rectal thermistor will measure core temperature. The heart rate monitor will measure the beats of the heart. Skin thermistors will measure the temperature of the skin surfaces. Laser doppler flow measure the relative units of blood flow velocity.

Galvanic skin response measures skin conductivity changes as individuals begin to sweat. Sweat is collected for assessment of sweat composition. Thermal perception is assessed for individual perception surrounding the temperature of the ambient environment. Nude body weight is measured to calculate sweat rate.

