# Statistical Analysis

#### Recruitment

Previous exercise research suggests that the difference in response of matched pairs is normally distributed with a standard deviation of 0.86. If the true difference of the mean response of matched pairs is 0.75, we will need to complete 12 experimental trials for each condition to be able to reject the null hypothesis that this response difference is zero with a power of 0.8. The Type I error probability associated with this test of the null hypothesis is 0.05.

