#### Interventions

A repeated measures two-way ANOVA (Time x condition) will be used for the dependent variables. If the F-ratio values are found to be significant, a Fisher's Least Significant Difference post hoc analysis will be conducted. A type I error probability of < 5% will be considered significant (p< 0.05). All data will be analyzed using a combination of Microsoft Excel and the Statistical Package for the Social Sciences (SPSS).

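### The visible plan gives no exit from the heat chamber before minute 30, gives the recorded core temperature and heart rate no part in ending a walk, and does not say how a shortened walk would be analysed

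*Combined protocol and SAP*

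**What the plan says.** **Exposure and exit.** Under Visits 2 and 3 in the Research Plan, participants enter the chamber (38°C, 60% relative humidity) and walk for 30 minutes at 3.5 mph and 5% grade. The end of the session is described once: "After 30 minutes of walking, subjects will exit the chamber for removal of all skin and finger sensors".

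**What is measured.** The Research Plan has core temperature, skin temperature, skin blood flow, galvanic skin response and heart rate collected continuously at baseline and during exercise. These are described as measurements; no action is attached to any of them.

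**What is screened.** The readiness questionnaire, the forearm skin test and the resting blood pressure limit all belong to Visit 1, before any heat exposure.

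**What menthol is thought to do.** The Purpose and Rationale gives as its main response an "increase in heat conservation, resulting in a reduced exercise capacity due to fatigue associated with a rise in core body temperature". It also describes menthol as "mimicking a cool sensation in warm environments". The same section says that menthol may help performance in heat and that carry-over to over-the-counter products is not known.

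**Analysis.** Under Statistical Analysis, Interventions: "A repeated measures two-way ANOVA (Time x condition) will be used for the dependent variables". Excel and SPSS are named. Nothing is said about missing time points, shortened sessions or replacement of participants.

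**Sample size.** Under Recruitment: "we will need to complete 12 experimental trials for each condition", for a power of 0.8. The Participants section gives 12 to 15 subjects and no attrition allowance.

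**The concern.** There are two separate gaps, and they should not be run together.

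**Safety.** On the plan's own account, menthol may increase heat storage while making the participant feel cooler. If so, the participant's own sense of overheating is a weaker warning in one of the two conditions. The plan acquires signals that do not depend on that sensation but, in the text available, gives them no part in deciding when a walk ends.

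**Analysis.** If a walk does end early, for whatever reason, the plan does not say how it is recorded or analysed. A within-subject ANOVA on a complete Time x condition layout needs every cell, so a missing late time point at one visit removes the participant's data from both. Sweat rate from body weight before and after exercise would also compare sessions of unequal length. With a target of 12 completed pairs, each loss matters, and loss may be related to condition and to core temperature.

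**Working it through.** **1. The sections side by side**

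| Section | Content | Link to ending a walk |
|---|---|---|
| Purpose and Rationale | Heat conservation and rising core temperature; cool sensation | Describes a possible risk; no procedure |
| Research Plan, general description | Core temperature and heart rate collected continuously | None stated |
| Research Plan, Visit 1 | Questionnaire, skin test, blood pressure | Before heat exposure only |
| Research Plan, Visits 2 and 3 | 30-minute walk, then exit | Elapsed time only |
| Statistical Analysis, Interventions | Time x condition ANOVA | No rule for a shortened walk |

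**2. Reproducing the plan's sample size**

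Inputs from Recruitment: a mean paired difference of 0.75, an SD of the paired differences of 0.86, and alpha: "The Type I error probability associated with this test of the null hypothesis is 0.05". Sidedness is not stated; two-sided is assumed.

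- Standardised difference: d = 0.75 / 0.86 = 0.872.
- Power = P(|T| > t(0.975, n − 1)), where T is noncentral t with n − 1 degrees of freedom and noncentrality d√n.
- At n = 12: noncentrality 0.872 × √12 = 3.02, critical value 2.201, power 0.785.
- At n = 13: power 0.823. This is the smallest n that reaches 0.80.

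The plan's 12 is therefore reproduced to within one participant.

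**3. What each lost pair costs**

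The same formula with fewer complete pairs, losses taken as unrelated to the response:

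| Complete pairs | Power, two-sided | Power, one-sided |
|---|---|---|
| 15 | 0.881 | 0.941 |
| 12 | 0.785 | 0.882 |
| 11 | 0.741 | 0.852 |
| 10 | 0.690 | 0.815 |

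From 12 pairs, the first loss costs 0.785 − 0.741 = 0.044 and the second a further 0.741 − 0.690 = 0.051.

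**4. Which way would selective loss push the result?**

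Suppose a walk ends when perceived heat strain passes some level. Let menthol raise core temperature by δ and lower perceived strain by an amount equivalent to m. Relative to control, the perceived signal under menthol shifts by δ − m.

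- m < δ: more early stops under menthol.
- m = δ: equal stops in both conditions.
- m > δ: fewer early stops under menthol.

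The documents give neither δ nor m, so the direction cannot be determined.

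**The case against.** **The two gaps need opposite facts.** Followed literally, everyone walks to minute 30 and no cell is empty; the analysis problem arises only if walks end early, which no section describes. This is right, and it is why they are kept as separate points.

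**A rule may exist elsewhere.** One passage and any consent pages were removed before review. This stands: the finding concerns the visible text only.

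**The plan does not predict harm.** The rationale also mentions a possible performance benefit, calls the carry-over to commercial products unknown, and states no directional hypothesis. This stands. A reader might infer that the plan expects BioFreeze to raise core temperature in this trial; it describes that response as the most salient one but does not commit to it.

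**Rationale and procedure do not contradict each other.** Strictly so. The gap is that a risk raised in one section is not taken up in the others.

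**The ANOVA loss is inferred.** The plan names no SPSS procedure, and minutes 10, 20 and 30 are fixed only for laser Doppler. Other outcomes might be analysed at times before a stop. If 15 enrol, three losses still leave 12 pairs. These points limit the size of the problem, but neither choice is written down.

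**A tempting stronger reading.** A reader might infer that those lost would be mainly BioFreeze walks with the largest temperature rise, so that the effect is diluted. That does not follow. In an illustration with assumed inputs (control rise 1.2°C, between-person SD 0.3, within-person SD 0.15, true effect 0.2°C), the complete-pair estimate is 0.177 to 0.195°C if stops track core temperature. It is 0.200°C if menthol masks the equivalent of 0.2°C, and 0.201 to about 0.21°C if it masks 0.4°C. None of these inputs is in the documents, so neither dilution nor excess BioFreeze loss should be claimed.

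**Conclusion.** The point holds in two limited parts.

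- **Safety.** In the visible text, elapsed time is the only stated exit. Core temperature and heart rate have no stated role in ending a walk, although the rationale raises both heat storage and a masking cool sensation. No probability of harm can be derived from the documents, and none is claimed.
- **Analysis.** How a shortened walk is handled is unspecified, and the default reading of the planned ANOVA discards both visits. Losing one or two of 12 pairs lowers two-sided power from 0.785 to 0.741 or 0.690.

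The power figures assume a two-sided paired t-test, losses unrelated to response, and the plan's 0.75 and 0.86, which are not tied to a named outcome. They indicate the cost of lost pairs rather than the exact power of the Time x condition test. The early-stop rate is unknown, and bias could run either way or be absent.

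**What to change.** **Protocol.** The investigator and ethics board should reconcile the Purpose and Rationale with the Research Plan by stating, or cross-referencing if it is held elsewhere, how the readings already recorded bear on ending a session, in the same way for both conditions. No criterion is proposed here; that is theirs to set.

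**Data and analysis.**
- Record the time and reason of every early stop, and report early stops by condition.
- Analyse serial outcomes with a mixed model using all observed time points, so that a shortened walk keeps its data up to the stop and the other visit is retained.
- Express sweat rate per minute actually exercised.

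**Cost.** Some protocol wording, a field for stop time and reason on the data sheet, and slightly more analysis work. No new equipment is needed, since the signals are already acquired. The mixed model relies on data being missing at random given what was observed; that cannot be verified, so the early-stop counts and reasons should be reported beside the results.

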#### Research Plan

Three experimental visits to the laboratory will be conducted. All visits will take place at the University of Nebraska at Omaha, Exercise Physiology Laboratory. Visit 1 will consist of the physical activity readiness questionnaire (PARQ), adverse reaction to BioFreeze, and body composition (hydrostatic weigh, bioelectrical impedance). Visits 2 and 3 will be separated by 7-14 days, randomized, and counterbalanced for experimental (BioFreeze) and control (hypoallergenic cream) trials. Both the experimental and control visits will follow the same protocol.

Participants will arrive following an overnight fast state while also refraining from strenuous activity, alcohol consumption, tobacco use, and recreational drugs for the previous 24-hour period. During these visit researchers will apply BioFreeze using a gloved hand from shoulder to wrist and mid-thigh to ankle (areas outside of the clothing). A hypoallergenic cream will be applied during the control visit.

Exercise will consist of 30 min of moderate intensity treadmill walking (3.5 mph at 5% grade) within a heated temperature/humidity-controlled chamber (38°C, 60% relative humidity).

Participants will be weighed before, and after completion of the exercise calculate sweat rate. Prior to the exercise session, participants will sit for 5 min in an ambient room temperature environment as a baseline. During baseline and during the exercise core temperature, skin temperature, laser doppler blood flow, galvanic skin response, and heart rate will be collected continuously. Sweat patches will be adhered to the forehead during exercise at minute 10 for collection of sweat composition over the next 10-20 minutes.

Thermal perception using the ASHRAE scale (cold to hot) will be assessed pre and during exercise.

### VISIT 1

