Visit 1 will take approximately 1 hour. Informed consent will be given. Participants will then complete the physical activity readiness questionnaire (PARQ) to be cleared for physical activity. Participants will have a small amount of the BioFreeze cream applied to a small area of the forearm (~2 x 2 in) to test for any adverse reaction over a period of 15 minutes. This initial skin reaction test is not a part of the research protocol. Then, resting blood pressure will be taken. Those without a reaction, and a resting blood pressure lower than 140/90, will have height, weight, and body fat composition measured. Height and weight will be measured using a medical scale and stadiometer, respectively. Body fat will be assessed with hydrostatic weighing using an electronic load cell-based system (Exertech, Dresbach, MN) correcting for residual lung volume or via a bio-electrical impedance analyzer (InBodyUSA, Cerritos, CA).

## VISITS 2 AND 3

Visits 2 and 3 will take approximately 2 hours each. Upon arrival at the lab, a nude body weight will be collected with the subject in a private room. While still in the room, subjects will self-insert a rectal thermistor 12-15 cm beyond the anal sphincter and don a chest strap heart rate monitor. After dressing in their exercise clothing, subjects will exit the private room so that chest, forearm, and calf thermistors can be adhered to the skin with tape.

Laser doppler flow (forearm and or/finger) will be adhered with tape and galvanic skin response (fingers) will be adhered using Velcro straps to the skin. Measuring instruments will be recorded using an integrated digital to analog converter (ADInstruments, Colorado Springs, CO).

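### Product is applied between the two nude weighings, so any residue lowers calculated sweat loss and a between-product difference biases the sweat-rate contrast: a minor point, cheaply fixed

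*Combined protocol and SAP*

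**What the plan says.** The Research Plan (Visits 2 and 3) fixes the order of events.

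- First weight: "Upon arrival at the lab, a nude body weight will be collected with the subject in a private room".
- Instrumentation and a 5-minute seated baseline follow. Then: "Immediately after, a researcher with gloved hands will topically apply BioFreeze or the control hypoallergenic cream from the shoulder to wrist and mid-thigh to ankle".
- After the 30-minute walk in the chamber and removal of the sensors, "a final nude body weight will be recorded after toweling off".
- Purpose of the two weights: "Nude body weight is measured to calculate sweat rate".

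No weight is taken between application and exercise. The earlier overview in the Research Plan says only that participants are weighed before and after exercise, which is less specific and does not conflict with this order.

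The comparator is a different product: "A hypoallergenic cream will be applied during the control visit". The Abstract calls it a gel. The plan states no applied mass for either product, and no weighing of product or towels. It has no wash-off step and no correction for residue. Toweling is the only step that could remove product, and it is not described further.

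**The concern.** Sweat rate is found by subtraction, so anything added to the body between the two weights and still there at the second one reduces the apparent loss. Here the added material is the intervention itself, spread over a large skin area. If both products left the same residue, the error would cancel in the within-person comparison and only the absolute sweat rates would be too low. Nothing in the plan makes the residues equal.

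A difference in residue belongs to the condition, not to the visit, so randomising and counterbalancing the order cannot remove it. The Purpose and Rationale section expects menthol to increase heat conservation. If more BioFreeze than control stayed on the skin, the artefact would look like less sweating and could be read as that effect. If more control stayed on, it could conceal such an effect.

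**Working it through.** **The plan's own figure.** The only quantitative planning figure is in Recruitment: "the difference in response of matched pairs is normally distributed with a standard deviation of 0.86", with a mean difference of 0.75, power 0.8 and alpha 0.05, giving 12 trials per condition. Sidedness is not stated; two-sided is assumed.

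- Normal approximation: n = (0.86 × (1.960 + 0.842) / 0.75)² = 10.3, so 11.
- Exact paired t: power is 0.785 at n = 12 and 0.823 at n = 13.

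The stated 12 is reproduced closely enough. It does not depend on this point. The 0.86 carries no unit and no named outcome, so it cannot serve as the SD for sweat loss.

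**Mass balance.** Let L be true loss and m the product left on the skin at the final weight.

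- Measured loss = arrival weight − final weight = L − m.
- BioFreeze minus control, measured = (L_B − L_C) − (m_B − m_C).
- Bias in the contrast = −(m_B − m_C). It is zero if the residues are equal.

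Product that evaporates, drips or is toweled off before the second weight is not part of m.

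**Conversion to a rate.** The walk lasts 30 minutes, so 1 g of residue is 1 / 0.5 = 2 g/h. Differences of 5, 10 and 20 g shift the contrast by 0.01, 0.02 and 0.04 kg/h.

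**Relative size.** The loss is assumed to be 300-700 g in 30 minutes, since the documents give none. A difference of 5 g is then 5/700 to 5/300 = 0.7-1.7% of loss, and 20 g is 20/700 to 20/300 = 2.9-6.7%.

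**Effect on the test.** There is one sweat rate per visit, so the condition comparison is taken as a two-sided paired t-test at 0.05. With n = 12 and no true effect, the noncentrality is b√12 / s, where b is the residue difference and s the paired SD. Both are assumed. Probability of p < 0.05:

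| Residue difference b | s = 30 g | s = 50 g | s = 75 g |
|---|---|---|---|
| 0 g | 5.0% | 5.0% | 5.0% |
| 2 g | 5.5% | 5.2% | 5.1% |
| 5 g | 8.3% | 6.2% | 5.5% |
| 10 g | 18.4% | 9.7% | 7.1% |
| 20 g | 55.8% | 24.5% | 13.5% |

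As an example, b = 10 and s = 50 give noncentrality 10 × 3.464 / 50 = 0.69 and rejection 9.7%. At n = 15, the upper end of the range in Participants, the same case gives 11.2%.

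**Masking.** By the same equation, a residue difference that offsets a true difference in sweat loss shrinks the measured contrast, and one of equal size cancels it.

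**The case against.** The strongest reply is that the size is entirely assumed. No mass, sweat loss or relevant SD is in the documents, and what counts is the difference in residue after toweling, not the amount applied. Nothing makes 20 g more plausible than 2 g, and at 0-2 g the test is essentially at its nominal level. The plan requires toweling and says both trials follow the same protocol. Sweating and dripping will also carry some product away. All of this stands, and it limits how serious the point can be. It does not show that the residues are equal, because the towel step is not standardised and the products differ.

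A second reply is that sweat rate is one of several outcomes and none is named primary. Core and skin temperature, skin blood flow, galvanic skin response, heart rate, sweat composition and thermal sensation do not use the nude weights. That also stands.

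A reader might infer that the plan carries a false-positive risk of 25% or 56%, or that it is likely to produce a spurious menthol effect. The documents support neither. Those figures belong to the largest assumed difference; the 56% also needs the smallest assumed SD. The direction of the bias is unknown. It is true that a larger sample would not remove the bias, but with 12-15 participants planned this changes little, as 9.7% against 11.2% shows.

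**Conclusion.** The point holds as a minor measurement weakness. The order of weighing and application is explicit, and the consequence is arithmetic: residue lowers calculated sweat loss, and unequal residue biases the sweat-rate contrast by that inequality. Whether the bias is negligible or material cannot be settled from the documents. Under the assumed ranges it runs from none to 0.04 kg/h, and the false-positive rate at n = 12 runs from nominal at 0-2 g to 14-56% at 20 g. The sign is unknown, so a true effect could be hidden as easily as a false one created. The sample size and the other outcomes are untouched. The change is worth making because it is nearly free and because the applied mass cannot be recovered afterwards.

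**What to change.** In the Research Plan, Visits 2 and 3:

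1. Weigh the product container before and after application at both visits and record the difference as the applied mass.
2. Before the final nude weight, remove product from the treated limbs and dry them fully, by one identical, timed procedure at both visits.
3. In Statistical Analysis, add a sensitivity analysis of sweat rate with corrected loss = measured loss + residue. Vary the residue from zero to the recorded applied mass, and include the cases where the two conditions sit at opposite ends. Describe it as a worst-case bound: toweling, dripping and evaporation make the true residue smaller, so the bound may be wide.

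Moving the first weight to after application would not be enough by itself, since product later lost or wiped away would then be counted as sweat.

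The cost is a few minutes and two container weighings per visit. If a damp wipe is used, there is a short delay before weighing and a risk of added moisture, hence the full drying and fixed timing.

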#### **Abstract**

The purpose of this study is to examine the human thermoregulatory impact of applying a commercially available menthol gel (BioFreeze) to the skin prior to moderate intensity walking under heated conditions. Eligible participants will be aged 19-45 years, have no previously known adverse reactions to menthol (active ingredient in BioFreeze) based upon a self-report, no adverse reactions to BioFreeze as determined through gel application to a small forearm area, and cleared for physical activity via the 2022 Physical Activity Readiness Questionnaire (PARQ). There will be a total of 3 experimental visits to the laboratory. Visit 1 will test for adverse BioFreeze reaction by applying a small amount of gel to the forearm (~2 x 2 in). Anthropometric and body composition data will also be collected at this time. Visits 2 and 3 will consist of 30 min of treadmill walking at a moderate pace (3.5 mph, 5% grade) under hot conditions (38°C, 60%RH). Visits 2 and 3 will be randomized and counterbalanced for BioFreeze or a hypoallergenic gel (control) application. Gels will be applied to areas commonly exposed during outdoor activity in warm conditions (shoulder to wrist, mid-thigh to ankle). Accordingly, participants will wear shorts and a tank top shirt during exercise. Core temperature, skin temperature, galvanic skin response, laser doppler blood flow, and heart rate will be continuously recorded throughout the exercise bout via an integrated analog to digital converter. Sweat will be collected during exercise using commercially available absorbent patches. Thermal sensation will be assessed throughout exercise via the ASHRAE thermal sensation likert scale (cold to hot). Lastly, nude body weight will be recorded pre and post exercise for sweat rate determination. The BioFreeze and control trials will be separated by a 7 to 14 day washout period.

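### Thermal perception rests on one scale that stops at 'hot' and whose rated object is unsettled (the room or the person), so cooling felt from the gel may be under-recorded by an unknown amount

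*Combined protocol and SAP*

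**What the plan says.** The Purpose and Rationale section states the aim as "to examine the impact of applying a menthol-based gel to the skin on human thermoregulation and thermal perception during exercise in the heat". Perception is therefore part of the purpose itself.

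One instrument serves that part. The Research Plan says: "Thermal perception using the ASHRAE scale (cold to hot) will be assessed pre and during exercise". No second perception item, limb-specific rating or comfort scale is described, and nothing is said about ratings at the top category. The number of scale points, the wording put to participants and the exact rating times are not given.

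The rated object is described once, in the closing explanation of Visits 2 and 3: "Thermal perception is assessed for individual perception surrounding the temperature of the ambient environment". The Abstract uses another label and names no object: "Thermal sensation will be assessed throughout exercise via the ASHRAE thermal sensation likert scale (cold to hot".

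The environment is the same on both days. "Subjects will then enter the heat chamber (38°C, 60% relative humidity) and immediately begin a 30-minute walk on a treadmill", and "Both the experimental and control visits will follow the same protocol". The gel goes on the limbs only, shoulder to wrist and mid-thigh to ankle. The Rationale expects that "menthol exerts a physiological response that is perceived as external cooling".

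**The concern.** Two features of the measure could each pull the observed difference between gels toward zero.

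- **Rated object.** The proposed mechanism starts in the treated skin. Someone asked about the room may feel cooler limbs and still report a hot room. Because the Abstract and the Visits 2 and 3 text describe the rating differently and no script is given, the question could also vary between staff or between a participant's two visits.
- **Top category.** Ratings are taken during a 30-minute uphill walk at 38°C. Any sensation beyond 'hot' is recorded as 'hot'. If control ratings gather there, the difference from BioFreeze is compressed. If ratings climb during the walk, the compression grows with time and alters the Time x condition pattern that the ANOVA is meant to test.

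The stake is how a null perception result would be read. It could mean that the product does not change perception, or that the question and scale could not show the change. Neither problem can be repaired in the analysis.

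**Working it through.** **1. The plan's own figure.** The Recruitment paragraph of the Statistical Analysis gives a paired difference of 0.75, SD 0.86, 12 trials per condition, power 0.8 and alpha 0.05 (sidedness not stated; two-sided assumed here). The standardised effect is 0.75 / 0.86 = 0.872. For a paired t-test with n = 12, the noncentrality is 0.872 × √12 = 3.02 on 11 degrees of freedom, which gives power 0.785. At n = 13 it is 0.823. The stated figure is reproduced to within rounding.

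**2. The rated object.** No arithmetic applies. The Abstract names a sensation scale without an object. The Visits 2 and 3 explanation names the ambient temperature, which is held constant. The Rationale locates the effect in the skin. These three texts do not settle what the participant is asked.

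**3. The top category (illustration).** The documents contain no rating data, so these assumptions are needed:

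- 0.75 and 0.86 are scale points. The plan does not name the outcome or unit behind them.
- The scale has 7 points with 'hot' at +3, and ratings are whole points.
- The between-person SD is 0.6. The within-visit SD is 0.86 / √2 = 0.608, so that the paired difference has SD 0.86.
- n = 12, two-sided paired t-test at 0.05, 40,000 simulated trials per row.

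Each uncapped rating is a mean plus a person effect plus visit noise. BioFreeze is 0.75 lower. Ratings are then rounded and capped at +3, or at +5 if two categories are added above 'hot'.

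| Uncapped control mean | Control ratings at 'hot' | Observed difference, cap +3 | Power, cap +3 | Power, cap +5 |
|---|---|---|---|---|
| 1.0 | 4% | 0.75 | 0.70 | 0.70 |
| 1.5 | 12% | 0.74 | 0.69 | 0.70 |
| 2.0 | 28% | 0.71 | 0.68 | 0.70 |
| 2.5 | 50% | 0.64 | 0.64 | 0.69 |
| 3.0 | 72% | 0.50 | 0.53 | 0.69 |
| 3.5 | 88% | 0.33 | 0.33 | 0.69 |
| 4.0 | 96% | 0.17 | 0.09 | 0.68 |

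The right comparator is about 0.70, not 0.785, because rounding to whole points costs some power whatever the cap. With 15 participants, the upper end of the planned 12-15, power under the +3 cap in the last three rows is 0.66, 0.46 and 0.16.

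**The case against.** The strongest reply is that the sentence about the ambient environment is one of several lay explanations of what each measurement is for. It is not an item script, and the Abstract's sensation label suggests that staff may in practice ask how the participant feels. This stands. The documents support calling the rated object inconsistent and unscripted. They do not show that the wrong question will be asked.

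A reader might infer that a fixed room must produce the same answer at both visits, whichever gel is on. The documents do not support that. The text speaks of individual perception, not an estimate of air temperature, and the Rationale describes menthol's effect as one perceived as external cooling. Perceived warmth can differ between gels in the same room. The item may be blunted, but it is not insensitive by definition.

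A reader might also infer that control ratings will sit at the top. This is plausible for walking uphill at 38°C, but the documents give no distribution of ratings. The table shows almost no loss up to 28% of control ratings at 'hot', a small one at 50%, and a large one only at about 70% or more.

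Finally, extra categories and a limb rating go beyond the named scale, and a limb rating adds an outcome in a small study whose Statistical Analysis has no multiplicity plan. That is a fair cost, and it is a reason to label the limb item secondary.

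**Conclusion.** The concern holds as a caution about a stated aim. One measure serves thermal perception, its object is described inconsistently, and its top anchor is 'hot' in a test carried out in heat. Both features, where they act, push the gel difference toward zero.

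The size is unknown. In the illustration, power against a comparator of about 0.68-0.70 ranges from no loss (control mean 1.0) through 0.53 (control mean at the top category) to 0.09 (one point above it). Those figures depend on treating 0.75 and 0.86 as scale points, on a 7-point whole-point scale and on a between-person SD of 0.6, so they are not an estimate of this trial's loss. The effect of asking about the room cannot be quantified from the documents. Core and skin temperature, blood flow, heart rate, galvanic skin response and sweat measures are untouched.

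**What to change.** - Replace the ambient-environment sentence in Visits 2 and 3 with one scripted, body-referenced question read identically at both visits, for example 'How do you feel (hot/cold) right now?'. Align the Abstract with it.
- Make whole-body sensation the main perception item. Add a rating of the treated arms and legs, labelled secondary.
- Use a version of the scale with categories above 'hot', such as 'very hot' and 'extremely hot', and state the number of points.
- Fix the rating times: after gel application and before chamber entry, then at 10, 20 and 30 minutes, when the arm is already held still for the laser Doppler reading.

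The cost is a question card and a few seconds per rating. Ratings above 'hot' must be collapsed when comparing with studies that used the standard scale, and the limb item adds one outcome.
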